11 STATISTICAL CONSIDERATIONS

The material of this section of the Clinical Trial Protocol is the basis for the SAP for the study which will provide accurate definitions and detailed specifications for the analyses to be performed on the data collected from this study.

11.1 DETERMINATION OF SAMPLE SIZE

It is anticipated that approximately 63 patients will be enrolled into this study.

This study is separated into 2 parts:

Part 1:

Each dose level 90 mg/m² D1D8 q3w and 120 mg/m² D1D8 q3w will include in parallel 14 patients overexpressing CA6.

Based on efficacy and safety (including predefined safety criteria), 1 dose will be selected during the interim analysis at the end of the Part 1 if the futility criteria on ORR is not met and will be continued in Part 2.

Part 2:

Part 2a: An additional 15 patients overexpressing CA6 will be treated in the expansion cohort at the selected dose.

Part 2b: In parallel, 20 patients will be treated at the selected dose in a mild CA6 expression cohort.

11.1.1 Sample size determination for Part 1 and Part 2a

The sample size calculation is based on efficacy criteria (ORR).

A 2-stage design will be used for the selected dose. It is expected that a beneficial ORR under SAR566658 is of at least 30% (H₁). An ORR of 12% (or less) will be considered as clinically non relevant (H₀). On the basis of these assumptions, 29 treated patients at the selected dose at the end of Part 2a would be necessary to reject the null response rate of 12% with a global power of 80% and a 1-sided alpha level of 10%. The calculation takes into account 1 interim analysis using a gamma (-2) beta spending function for futility analysis and a Lan-DeMets (OF) alpha spending function in a 1 sample test for a binomial proportion.

An interim analysis is planned in Part 1 after 14 patients are treated at each dose. If at least 2 responses over the first 14 patients are observed, then 15 other patients will be treated in Part 2a at the selected dose, if the safety profile is tolerable.

A total of 7 confirmed responses (CR or PR) or more out of 29 patients (14 patients from Part 1 and 15 patients from Part 2a at the selected dose) will be necessary to reject the null hypothesis at the end of the Part 2a expansion cohort.

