6.1.2.1 Part 2a

The expansion/overexpressing CA6 cohort with an additional 15 metastatic TNBC patients with CA6 overexpression (membrane intensity of 2+, 3+ in $\geq 30\%$ of tumor cells) will start at the selected dose using the same selection criteria as for Part 1. If at least 7 confirmed responses (PR or CR) are seen among the 29 patients, then the null hypothesis of 12% ORR can be rejected. This test has a 1-sided type 1 error of 10% and 80% power for an alternative hypothesis of 30% response rate.

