11.4.4.4 Multiplicity considerations

No adjustment for multiplicity linked to the selection of dose will be done.

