11.5 INTERIM ANALYSIS

Interim analyses of efficacy, safety, and other data will be performed after 14 patients are treated at each dose level at the end of Part 1. These interim analyses are planned to occur when all patients have completed at least 4 postbaseline tumor assessments, experienced confirmed objective response, or discontinued the study for any reason. However, if the futility criteria of 2 responders is either met or not met with certainty for both arms when all patients have completed 2 postbaseline tumor assessments, experienced confirmed objective response, or discontinued the study for any reason, the analyses may be conducted at that time instead. Enrollment will be interrupted after completion of enrollment in Part 1, until completion of the Part 1 interim analysis.

An interim analysis based on efficacy will be performed to assess futility (to reject early the hypothesis that the response rate is 30%). If there is 0 or 1 response (CR or PR) in the first 14 patients treated at each dose, the 7.1% critical boundary is not met and the alternative hypothesis of at least 30% will be rejected. If the critical boundary of 7.1% is reached (2 responses or more), the study can continue in Part 2 at the selected dose.

At the same interim analysis, overwhelming efficacy will be assessed (to reject early that the response rate is less than or equal to 12%). If there are 6 responses or more in the first 14 patients treated at 1 dose, the critical boundary of 42.9% (1-sided nominal significance level of 1.8%) is reached and the null hypothesis of 12% will be rejected.

Overall, this procedure has 80% statistical power (1-sided alpha level of 10%) to reject the null hypothesis, using a gamma (-2) beta spending function for futility analysis and a Lan-DeMets (OF) alpha spending function in a 1 sample test for a binomial proportion (East version 6.3 using exact computations, Cytel Software, Cambridge, MA).

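### The stated 80% power and 10% type I error describe a test at one pre-chosen dose, not the select-then-test procedure that will be run

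*Protocol*

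**What the plan says.** Protocol 11.1.1 sets the hypotheses: "An ORR of 12% (or less) will be considered as clinically non relevant" is the null, and for the alternative "It is expected that a beneficial ORR under SAR566658 is of at least 30" percent. It states that "A 2-stage design will be used for the selected dose" and that 29 patients give the design its properties "with a global power of 80% and a 1-sided alpha level of 10" percent, based on a one-sample binomial test with one interim look. Protocol 6.1.2.1 puts it more flatly: "This test has a 1-sided type 1 error of 10% and 80% power for an alternative hypothesis of 30% response rate". Protocol 11.5 says: "Overall, this procedure has 80% statistical power (1-sided alpha level of 10%) to reject the null hypothesis". SAP 1.1, 1.3.2 and 3 repeat these statements, and so does the protocol synopsis.

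The dose is not fixed in advance. Protocol 6.3 and SAP 1.1 randomize 14 patients to each of 90 and 120 mg/m² and drop a dose with fewer than 2 responses. They take 90 mg/m² when ORR and safety are comparable, and 120 mg/m² when its ORR is higher and safety is comparable. The 14 Part 1 patients at the chosen dose then count among the final 29. Comparable ORR has no numeric meaning in either document. Protocol 11.4.4.4 and SAP 2.4.4.3 say: "No adjustment for multiplicity linked to the selection of dose will be done".

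**The concern.** The words global and procedure invite the reader to take 80% and 10% as properties of everything from randomization to the final test. The calculation behind them has no selection step. Selection acts on both error rates. Two chances to look good raise the false-positive rate, and a rule that favors 90 mg/m² can send the trial forward with a dose that then fails even though the other would have passed. A sponsor or ethics reader would want the chance of success for the design actually run. The decision not to adjust for dose selection also needs a number to support it, and the documents give none.

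**Working it through.** **Inputs.** Null 12%, alternative 30%, final rule at least 7 of 29 (Protocol 11.1.1). At the interim, 14 patients per dose, futility at 0 or 1 response, early rejection at 6 or more (Protocol 11.5, SAP 3). Selection rules from Protocol 6.3.

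**Step 1: one fixed dose.** Let b(x; 14, p) be the binomial probability of x responses in 14. Let R(x, p) be the chance of rejecting after seeing x:

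- R = 0 for x ≤ 1
- R = 1 for x ≥ 6
- R = P(Bin(15, p) ≥ 7 − x) for x = 2 to 5

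P(reject) = Σ b(x; 14, p) · R(x, p).

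| x | b at 30% | R at 30% | product | b at 12% | R at 12% | product |
|---|---|---|---|---|---|---|
| 2 | 0.1134 | 0.4845 | 0.0549 | 0.2826 | 0.0265 | 0.0075 |
| 3 | 0.1943 | 0.7031 | 0.1366 | 0.1542 | 0.0959 | 0.0148 |
| 4 | 0.2290 | 0.8732 | 0.2000 | 0.0578 | 0.2654 | 0.0153 |
| 5 | 0.1963 | 0.9647 | 0.1894 | 0.0158 | 0.5524 | 0.0087 |
| ≥6 | 0.2195 | 1 | 0.2195 | 0.0038 | 1 | 0.0038 |
| Sum | | | **0.8004** | | | **0.0501** |

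The stated 80% is reproduced. The attained type I error is 5.0%. The gap to 10% comes from discreteness: lowering the final cutoff to 6 of 29 would give 11.7% with the same interim rules (12.7% as a single-stage test), so 7 of 29 is the smallest cutoff that respects the level.

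**Step 2: select, then test.** Let x be the responses at 90 mg/m² and y those at 120 mg/m², independent Binomial(14). A dose needs at least 2 to be eligible. If both are eligible, 120 mg/m² is chosen when y − x > m, otherwise 90 mg/m². Here m is the largest lead still called comparable. Safety is assumed comparable. Then

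P(select 120 and reject) = Σ b(x; 14, p90) · b(y; 14, p120) · 1{120 chosen} · R(y, p120),

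and likewise for 90 mg/m². With m = 0 (only exact ties go to 90 mg/m²):

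| True ORR, 90 / 120 | Select 90 | Select 120 | Stop | Select 90 and reject | Select 120 and reject | Any rejection |
|---|---|---|---|---|---|---|
| 12% / 12% | 0.4356 | 0.3284 | 0.2361 | 0.0469 | 0.0415 | **0.0884** |
| 12% / 30% | 0.1498 | 0.8272 | 0.0231 | 0.0257 | **0.7209** | 0.7466 |
| 5% / 30% | 0.0315 | 0.9283 | 0.0402 | 0.0002 | **0.7870** | 0.7872 |
| 30% / 12% | 0.9059 | 0.0710 | 0.0231 | **0.7724** | 0.0163 | 0.7887 |
| 30% / 30% | 0.5798 | 0.4179 | 0.0023 | 0.5276 | 0.3915 | **0.9191** |

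**Step 3: is 8.8% the worst case?** R rises with x, so with both doses at 12% always taking the higher count maximizes rejection, and m = 0 does that. Any other rule, including one driven by safety, can only lower it (8.4% at m = 1).

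**Step 4: where the power goes in the 12% / 30% case.** Once 120 mg/m² is selected, the test rejects with probability 0.7209 / 0.8272 = 0.871. The loss against the fixed-dose figure, 0.8004 − 0.7209 = 0.0795, is the chance that 120 mg/m² would have passed but 90 mg/m² was taken forward.

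**Step 5: sensitivity to the meaning of comparable.** The values of m below are assumptions. If 120 mg/m² is credited whenever it alone reaches 6 of 14, power to select and reject for 120 mg/m² in the 12% / 30% case is 64.0% at m = 1, 55.5% at m = 2 and 50.1% at m = 3. Without that credit, m = 1 gives 63.8%. With both doses at 30% and the credit applied, power stays between 87.2% (m = 3) and 91.9% (m = 0).

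**The case against.** The strongest reply is that nothing was miscalculated. Protocol 11.1.1 ties the design to the selected dose and names a one-sample test, the 80% reproduces, and the absence of adjustment for selection is declared. This stands as far as it goes: the gap is in reporting, and the sample size is right for the test it describes. It does not cover the wording in 11.5, nor the flat statement of a 10% type I error in 6.1.2.1. The selected dose depends on the data, while the calculation treats it as fixed.

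A second reply is that 72.1% is a quantity the documents never claim, since it requires both selecting 120 mg/m² and rejecting. That is fair, and the any-rejection figure of 74.7% belongs beside it. The difference consists of rejections for a dose at the null rate. It is also fair that preferring 90 mg/m² when the doses look alike is deliberate, so part of the loss is a price the sponsor may accept.

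A reader might infer three stronger things that the documents do not support:

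- **That selection breaks the 10% level.** It does not: the maximum is 8.8%, and SAP 2.4.4.1 uses 0.1 as a test level, which is a ceiling.
- **That an inactive 90 mg/m² is the reason for the second arm.** Protocol 4.2 gives the early prophylaxis results and a PK simulation as the reasons, and it carries 90 mg/m² forward as the recommended dose.
- **That the trial is underpowered in general.** Power exceeds 80% when both doses are active.

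**Conclusion.** The point holds as a mislabeling of operating characteristics. The 80% belongs to one pre-chosen dose. That test has attained size 5.0%, and neither figure describes the procedure with selection. For the full procedure the false-positive rate is at most 8.8% with both doses at 12%. Power to select and reject is 72.1% when only 120 mg/m² is active and 90 mg/m² is at 12%, 78.7% if 90 mg/m² is at 5%, and 77.2% when only 90 mg/m² is active; the chance of rejecting is 91.9% when both are active.

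These figures assume comparable safety and that only exact ties go to 90 mg/m². The fall to about 64% at a one-responder margin rests on a margin the documents do not give. It shows how much the undefined word matters and does not predict the trial's power.

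**What to change.** In Protocol 6.1.2.1, 11.1.1 and 11.5 and SAP 1.1, 1.3.2 and 3, with the synopsis aligned:

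- Label 80% as the power for one pre-chosen dose.
- Replace the type I error of 10% with an attained size of 5.0% against a level of 10%.
- Add a short table of size and power for the full select-then-test procedure by pair of true ORRs, such as the five in Step 2. Compute it under the sponsor's own working meaning of comparable ORR, stated in the text, with the 6-of-14 rule applied.
- In Protocol 11.4.4.4 and SAP 2.4.4.3, cite the 8.8% maximum as the reason no adjustment is needed.

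The cost is a few sentences and one table. Sample size, boundaries and alpha level do not change. The stated power becomes less favorable where only one dose is active and more favorable where both are.

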11.1.2 Sample size determination for the mild CA6 expression cohort (Part 2b)

At the selected dose, the relationship between CA6 expression level and efficacy outcome will be assessed by adding a cohort of 20 patients with mild CA6 membrane staining (at least 1% positive tumor cells at intensity $\geq 1+$ and $< 30\%$ of tumor cells at intensity 2+, 3+).

With a sample size of 20 patients, a true response rate above 15% can be rejected with 83% confidence if we observe 0 or 1 response. Moreover, if we observe 7 responses over the 29 patients in the biomarker positive group ($\geq 30\%$, 2+,3+) and ≤ 1 response in the mild CA6 biomarker positive group (CA6 IHC = $< 30\%$ 2+,3+ and $\geq 1\%$, $\geq 1+$), the 1-sided p-value (according to Fisher's exact test) will be around 7%, suggesting an association between biomarker status and ORR.

11.2 DISPOSITION OF PATIENTS

The number of registered patients (patients who signed the informed consent) as well as the number and percentage of patients included in the analysis populations defined in [Section 11.3](#) will be provided.

[figure not shown]
Reasons for treatment discontinuation will be summarized using the all treated/safety population.

11.3 ANALYSIS POPULATIONS

Different analysis populations are described. The main populations are described below.

An overview of the analysis populations is presented in [Figure 1](#).

Figure 1 - Analysis population overview

11.3.1 Safety population

The all treated population consisting of patients who will actually receive at least 1 dose (or any partial) of SAR566658. This population is the primary population for the analyses of efficacy and safety parameters.

11.3.2 Evaluable for predefined selection criteria population (Part 1)

This population is only defined for Part 1.

Patients evaluable for predefined selection criteria will be defined as patients treated in the study who have completed 2 cycles or who experienced predefined safety criteria (whatever the dose received).

11.3.3 Response evaluable population

The response evaluable population will be defined as the patients of the all treated population, with measurable disease at study entry and with CA6 positivity according to the threshold defined in the relevant study part (Part 1 and Part 2a or Part 2b) and who had an evaluable response assessment during treatment (until 30 days after last SAR566658 administration). Treated patients who could not have a postbaseline tumor assessment because of early disease progression or early death due to progressive disease are also included in the response evaluable population.

Sensitivity analyses of the primary efficacy endpoint will be performed on the response evaluable population.

11.3.4 Preregistered population

The preregistered population is defined as the patients who signed the prescreening informed consent for CA6 assay assessment of their archival biopsy.

11.3.5 Registered population

The registered population is defined as the patients who concomitantly fulfill the following requirements:

- Signed screening informed consent for study participation.
- CA6 assay assessment of their archival tumor biopsy showing CA6 positivity according to the threshold defined in the relevant study part (Part 1 and Part 2a or Part 2b).

11.3.6 Enrolled population

The enrolled population includes registered patients who concomitantly have all inclusion/exclusion criteria verified. In addition, in Part 1, patients also need confirmation of a successful allocation of a randomization number through the IVRS/IWRS in order to be enrolled.

11.3.7 Pharmacokinetic population

The PK population will include all patients who received at least 1 dose of SAR566658, even if incomplete, and have data for at least 1 valid PK parameter available.

11.3.8 Evaluable population for immunogenicity

The evaluable population for immunogenicity will include all patients with at least 1 sample drawn postbaseline after study drug infusion (on-treatment period or follow-up) that is appropriate for ATA testing (patients with missing ATA at baseline will be considered evaluable).

11.4 STATISTICAL METHODS

A list of study endpoints and their definitions are provided in [Section 9](#).

Data will be presented by dose level. Unless otherwise specified, analyses will be descriptive and performed based on the all treated population. The baseline for a given parameter is defined as the last assessment for this parameter before the first SAR566658 administration.

Continuous data will be summarized using number of available data, mean, standard deviation, median, minimum, and maximum for each dose level. Categorical and ordinal data will be summarized using number and percentage of patients in each dose level.

11.4.1 Analysis of demographic and baseline characteristics

Standard demographic and baseline characteristics, medical/surgical history, cancer history including primary tumor type and histopathology type, time from first diagnosis to first study treatment administration, prior antitumor therapy and tumor characteristics (lesions location, number and type of organs involved), assessment of CA6 expression at study entry, and laboratory parameters (including hematology, coagulation, and blood chemistry) at baseline will be described. Results of ECG evaluations will also be described.

Parameters will be summarized by dose level and overall using descriptive statistics.

11.4.2 Extent of study treatment exposure and compliance

The extent of IMP exposure and compliance will be assessed and summarized by dose level within the all treated population.

11.4.2.1 Extent of investigational medicinal product exposure

The following variables will be calculated and summarized with descriptive statistics to describe exposure to SAR566658:

- Number of cycles started and duration of exposure in weeks, defined as $([\text{First day of last cycle} - \text{first day of first cycle} + 21 \text{ days}]/7)$.
- Cumulative dose (in mg/m^2), defined as the sum of all doses administered from first to last dose.
- Actual dose intensity, defined as the cumulative dose divided by the number of weeks on study.
- Relative dose intensity (in %), defined as the ratio of the actual dose intensity to the planned dose intensity. The relative dose intensity is an indicator of the feasibility of the chosen schedule of administration.
- Cycle delays: a dose at Day 22 (Day 1 of next cycle) is deemed to have been delayed if the study treatment is ≥ 4 days beyond the theoretical day of treatment.

- Dose reduction: for the second and subsequent infusions, a dose is deemed to have been reduced if the dose level a patient receives differs from the previous actual dose level. The first infusion will not be counted for a reduction.
- Infusion omission (Day 8): at a given infusion, dose omission will be considered if no drug is administered (dose=0 mg/m²). Number of dose omissions within a cycle will be equal to the difference between expected number of infusions and number infusions actually received.
- Dose interruption: administration of SAR566658 infusion is temporarily stopped during the infusion.

Dose information variables will be assessed for each patient and summarized descriptively (N, mean, standard deviation, median, minimum, and maximum). Analyses will be performed based on the number of patients and on the number of cycles.

11.4.3 Prior/concomitant medication/therapy

The following parameters regarding prior anticancer therapy will be summarized:

- For surgery and radiotherapy: time from last procedure to first infusion.
- For chemotherapy, gene therapy, immunotherapy, hormonal therapy, targeted therapy: time from last administration to first infusion of the IMP.

Medications will be summarized by treatment group according to the World Health Organization Drug Dictionary (WHO-DD), considering the first digit of the Anatomical Therapeutic Chemical (ATC) class (anatomic category) and the first 3 digits of the ATC class (therapeutic category). All ATC codes corresponding to a medication will be summarized. Patients will be counted once in each ATC category (anatomic or therapeutic) linked to the medication.

Further treatment of interest for the analysis and given to the patient after withdrawal from IMP will be listed.

11.4.4 Analyses of efficacy endpoints

11.4.4.1 Analysis of primary efficacy endpoint(s)

The primary efficacy endpoint (refer to [Section 9.1.2](#)) is the ORR defined as the proportion of patients confirmed a CR or PR as BOR according to RECIST 1.1, relative to the total number of patients in the response evaluable population.

The ORR will be estimated and provided with its 80% CI using an exact method.

The primary efficacy analyses will be performed on the all treated population and sensitivity analyses on the response evaluable population.

11.4.4.2 Analyses of secondary efficacy endpoints

The DCR (refer to [Section 9.2](#)) will be summarized with descriptive statistics. Confidence intervals at 95% will be computed using an exact method.

The median DOR, PFS, and TTP (refer to [Section 9.2](#)) with 95% CI will be analyzed using Kaplan-Meier methods.

11.4.4.3 Analyses between CA6 expression level and efficacy endpoint

The relationship between circulating CA6 at baseline, CA6 tumor expression level by IHC at baseline (Hscore, % staining cells at intensity 2+/3+), and BOR parameters (responders versus non responders) or tumor shrinkage will be explored. Logistic regression or log-linear multivariate analyses (depending on the endpoints) might be performed.

11.4.4.4 Multiplicity considerations

No adjustment for multiplicity linked to the selection of dose will be done.

11.4.5 Analyses of safety data

All safety analyses will be performed on the all treated population.

The safety analysis will be based on the reported AEs and other safety information, such as clinical laboratory data, vital signs, and ECG (see [Section 9.2.2](#)).

11.4.5.1 Observation period

The observation period will be divided into 3 periods:

- The **screening** period is defined as the time from the signed informed consent date up to the first treatment administration.
- The **treatment** period is defined as the time from the first treatment administration to the last treatment administration +30 days.
- The **posttreatment** period is defined as the period of time starting the day after the end of the treatment period.

11.4.5.2 Predefined selection criteria

Predefined selection criteria will be summarized by dose level during the first 2 cycles, but also at subsequent cycles. Details will be provided (characteristics of predefined selection criteria) by patient (see [Section 9.1.1](#)).

